## 8 Study Data Collection and Assessments

### 8.1 Primary Assessment

For the primary objectives of the study the following measurement data will be collected:

Measurements performed on Ligence Heart and comparator software manually (Part 1):

- AoS (PLA)
- RVB (A4CH)
- LVEDV (A4CH)
- LVEDV (A2CH)
- RVEDA (A4CH)
- RAA (A4CH)
- AV-Vmax
- TR-Vmax
- E
- S'RV
- DEC
- ACT
- AV-VTI
- TR-VTI
- LVEDV (A2CH + A4CH)

Measurements performed by automatic functionalities of Ligence Heart and the comparator – the same measurements performed by cardiologists (Part 2):

- RAMAD (A4CH)
- AoA
- AoS
- STJ
- AAo
- LAD (PLA)
- LAV
- IVSd
- LVPWd
- LVEDD
- LVESD
- LVEDV (A4CH)
- LVESV (A4CH)
- LVEDV (A2CH)
- LVESV (A2CH)

UAB Ligence	Clinical Investigation Report	2021-04-09
		Rev: 1.0

- RAA
- RVB
- RVM
- RVOTPD
- RVEDARVESA

## 8.2 Exploratory Assessments

The Principal Investigator collects descriptive statistics data from the enrolled subjects that have been enrolled before they are sent to the IT staff for pseudonymization. The following descriptive statistics data will be collected:

- Gender
- Age (years)
- Weight (kg)
- Height (cm)
- Ethnicity
- Ultrasound machine model
- Total number of DICOM files
- History of heart failure
- History of myocardial infarction
- History of percutaneous coronary intervention (PCI)
- History of open cardiac surgery
- Atrial fibrillation
- History of arterial hypertension
- History of valvular heart disease
- History of congenital heart disease
- History of cardiomyopathy
- History of implanted devices/closures/prostheses

## 8.3 Safety Assessments

The description, severity, and device relatedness of any AE or SAE during the study will be recorded. In the event of any device issues, the event will be recorded. Safety reporting will be conducted as described in this protocol.

# 9 Qualification and Training Plan

## 9.1 Staff Qualifications

The investigators are included in the clinical study if compliant with the following requirements:

- Investigators are appropriately qualified cardiologists and experienced in the performance of 2D TTE exams by using medical software with the same intended purpose Ligence Heart;
- Investigators have adequate time to comply to participate in the study and provide results that are up to the required quality and safety standards;
- Investigators are willing to comply with the clinical investigation plan;
- Investigators are willing to sign the appropriate clinical investigation agreement;
- Investigators have past experience with conducting clinical studies or appropriate training;
- Investigators are familiar with ISO 14155:2011 requirements.

## 9.2 Training Plan for the Protocol and Research Device/Product

UAB Ligence	Clinical Investigation Report	2021-04-09
		Rev: 1.0

Before starting the study, the study staff will be trained based on their role in the study on the clinical investigation requirements set forth in this study protocol according to the training plan, as follows:

*Protocol Training* – All study staff will be trained on the clinical investigation plan and, as applicable, on devices. Documentation of such training will be retained and provided together with the clinical investigation report.

*Training logistics* – CMO of UAB Ligence is responsible for conduct of the training.

*Target audience* – All site personnel involved with the conduct of the study will be trained on the protocol and, as necessary, on device use.

*Device Training* – All users will be trained on the Ligence Heart feature per the user manual.

IT staff of the investigational site directly operating or maintaining the research device will be trained based by the Sponsor during the training.

The Principal Investigator will be ultimately responsible for execution of this study in accordance with the protocol and for device/product use in this study by members of the study staff.

## 10 Safety

The description, severity, and study device relatedness of any AE or SAE during the study will be recorded. In the event of any study device issues, the issues will be recorded. Safety reporting will be conducted as described in this protocol.

### 10.1 Anticipated Adverse Events

No foreseen risks that could be considered adverse events could results from this study, as no direct contact with the patients will be held and no additional clinical procedures will be performed.

There is always a chance of unforeseen risks. Throughout the study, the Sponsor will evaluate and update safety information in study documents.

### 10.2 Adverse Event Definitions

**Adverse Event (AE):** any untoward medical occurrence, unintended disease or injury, or untoward clinical signs (including abnormal laboratory findings) in subjects, users or other persons, whether or not related to the investigational medical device [ISO 14155:2011 3.2]. This includes events related to the investigational device or the comparator and to the procedures involved. For users or other persons, this is restricted to events related to the investigational medical device.

**Serious Adverse Event (SAE):** an adverse event that led to death; led to a serious deterioration in the health of the subject, that either resulted in a life-threatening illness or injury, a permanent impairment of a body structure or a body function, or in-patient or prolonged hospitalization, or medical or surgical intervention to prevent life-threatening illness or injury or permanent impairment to body structure or a body function; or led to fetal distress, fetal death or a congenital abnormality or birth defect. Planned hospitalization for a pre-existing condition, or a procedure required by the protocol without serious deterioration in health, is not considered a SAE [ISO 14155:2011 3.37].

**Adverse Device Effect (ADE):** an adverse event related to the use of an investigational medical device [ISO 14155:2011 3.1]. This includes any adverse events resulting from insufficient or inadequate instructions for use, deployment, implantation, installation, or operation, or any malfunction of the investigational medical device. This includes any event that is a result of a user error or intentional misuse of the investigational device [ISO 14155:2011 3.43].

**Serious Adverse Device Effect (SADE):** an adverse device effect that has resulted in any of the consequences characteristic of a serious adverse event [ISO 14155:2011 3.36].

UAB Ligence	Clinical Investigation Report	2021-04-09
		Rev: 1.0

**Device deficiency:** an inadequacy of a medical device with respect to its identity, quality, durability, reliability, safety, or performance, such as malfunctions, use errors, and inadequate labelling [ISO 14155:2011 3.15].

**Unanticipated serious adverse device effect (USADE):** a serious adverse device effect, which by its nature, incidence, severity, or outcome has not been identified in the current version of the risk analysis report [ISO 14155:2011 3.42]. In the United States, any serious adverse effect on health or safety or any life-threatening problem or death caused by, or associated with, a device, if that effect, problem, or death was not previously identified in nature, severity, or degree of incidence in the study documents, will be reported in accordance with 21 CFR §812.3 and applicable laws and regulations.

### 10.3 Recording and reporting of Adverse Events

Adverse Event (AE) information will be collected throughout the study and reported to the Sponsor on the Adverse Event CRF. All Adverse Events, regardless of relatedness or outcome, must be reported. The investigator is responsible for reporting all AE to the Sponsor.

See the Adverse Event CRF for the information to be reported for each Adverse Event.

For Adverse Events that require immediate reporting, initial reporting may be done by phone, e-mail (contact the designated contact person for this clinical investigation), or on the CRF with as much information as is available.

The Adverse Event case report form:

MEDDEV 2.7/3 SAE Report Table- V1															
EUDAMED - ID:															
Title of Clinical Investigation:															
CIP Number:															
Contact person (Name, Address, E-Mail, Telephone Number)										Device type:					
MS+NCA Reference Numbers for all participating Countries:										Reference Member State:					
No. of Patients enrolled to date (date of report):										No. of Invest. Devices used to date					
Date of Report:															
Stat us: a, m, u	Date Spon sor recei ved Rep ort of SAE	Cou ntry	Stud y Cent er	Patie nt ID Cod e	Date of Proc edur e/ First Use	Date of Even t Ons et	Even t: Orga n Syst em	Desc ripti on of even t	actio n/ treat men t/ patie nt outc ome	Asse ssm ent of Rela tions hip to Proc edur e: Yes No Possi bly	Asse ssm ent of Rela tions hip to Inve stiga tion al Devi ce: Yes No Possi bly	Una ntici pate d SAD E yes/ No	Trea tme nt Arm: Inve stiga tion al Devi ce/ Cont rol Grou p/ blind ed/ n.a	Even t Stat us: Reso lved / Reso lved with Sequ elae / Ong oing / Deat h	Date of Even t Reso lutio n

UAB Ligence	Clinical Investigation Report	2021-04-09
		Rev: 1.0

## 10.4 Adverse Event and Device Deficiency review process

All Adverse Events and Device Deficiencies will be reviewed by the Sponsor's Investigation Management and/ or designee. This review will include the determination whether the Adverse Event/Device Deficiency meets regulatory reporting requirements. The sponsor will ensure timely Adverse Event/Device Deficiency reporting to meet global and country specific regulatory requirements.

**Table** Adverse Event Reporting Requirements

Serious Adverse Device Effects (SADE), including Unanticipated Serious Adverse Device Effect (USADE):	
Investigators submit to:	
Sponsor	As soon as possible, but in no case later than 3 calendar days after the clinical site study team first learns of the event or of new information in relation with an already reported event.
Regulatory Authority	Reporting timeframe as per local reporting requirement.
Sponsors submit to:	
Regulatory Authority	Reporting timeframe as per local reporting requirement.
Bioethics Committee	Reporting timeframe as per local reporting requirement.
Serious Adverse Events (SAE)	
Investigators submit to:	
Sponsor	As soon as possible, but in no case later than 3 calendar days after the clinical site study team first learns of the event or of new information in relation with an already reported event.
Regulatory Authority	Reporting timeframe as per local reporting requirement.
Sponsors submit to:	
Regulatory Authority	Reporting timeframe as per local reporting requirement.
Bioethics Committee	Reporting timeframe as per local reporting requirement.
Adverse Device Effects (ADE)	
Investigators submit to:	
Sponsor	As soon as possible, but in no case later than 3 calendar days after the clinical site study team first learns of the event.
Regulatory Authority	Reporting timeframe as per local reporting requirement.
Sponsors submit to:	
Regulatory Authority	Reporting timeframe as per local reporting requirement.
Bioethics Committee	Reporting timeframe as per local reporting requirement.
Device Deficiency with SADE potential	
Investigators submit to:	
Sponsor	As soon as possible, but in no case later than 3 calendar days after the clinical site study team first learns of the event or of new information in relation with an already reported event.
Regulatory Authority	Reporting timeframe as per local reporting requirement.
Sponsors submit to:	
Regulatory Authority	Reporting timeframe as per local reporting requirement.

UAB Ligence	Clinical Investigation Report	2021-04-09
		Rev: 1.0

Bioethics Committee	Reporting timeframe as per local reporting requirement.
All other Device Deficiencies	
Investigators submit to:	
Sponsor	Submit in a timely manner after the clinical site study team first learns of the deficiency.
Regulatory Authority	Reporting timeframe as per local reporting requirement.

## 10.5 Device Deficiencies/Complaints

Device deficiencies/complaints should be reported to the study Sponsor contact identified on the cover page of this protocol. All device deficiencies/complaints are to be collected, fully investigated, and documented together with the case report forms and summarized in the clinical investigation report. The Principal Investigator is responsible for notifying the Sponsor if there are any device issues that could potentially lead to a SAE.

## 11 Ethical Conduct of the Study

The study will be carried out in accordance with the protocol and with principles enunciated in the current version of the Declaration of Helsinki; the guidelines of Good Clinical Practice (GCP) for medical devices, as set forth by ISO 14155:2011 and ISO 14971:2010.

The study will be conducted and reported in accordance with applicable policies of the governing Ethics Committee (EC) and governing regulatory authorities.

If national or regional EC requirements are less strict than the requirements of GCP, such as ISO 14155:2011 for medical devices, the Sponsor shall make attempts to apply the requirements of this International Standard to the greatest extent possible, irrespective of any lesser requirements, and shall record such efforts.

### 11.1 Ethics Committee

The responsible Principal Investigator at each site will ensure that approval from an appropriately constituted EC is attained for the clinical study prior to enrolling subjects, and Principal Investigator and the Sponsor will ensure that documentation of approval is maintained for the duration of the study.

The Principal Investigator will ensure that the Sponsor is notified of any withdrawal of EC approval within 5 working days of such occurrence. If approval is terminated or suspended, the Principal Investigator will promptly notify the Sponsor and provide written explanation.

Documents, which are provided to the responsible Bioethics Committee for review:

- Application for biomedical research;
- Reasoning for disbandment of Informed Consent forms;
- Application for a permission for clinical investigation;
- Research protocol;
- Documentation on the medical device.

Bioethics Committee approval of the biomedical clinical investigation must be received before commencement of the biomedical clinical investigation at the investigation site. The approval letter must contain enough information to identify the version or date of the documents approved.

### 11.2 Regulatory Agencies and Competent Authority(ies)

UAB Ligence	Clinical Investigation Report	2021-04-09
		Rev: 1.0

All the previously mentioned documents provided to the EC will be reviewed by the State Health Care Accreditation Agency prior to the final decision of the EC.

### 11.3 Management of Protocol Modifications and Amendments

Substantial amendments will only be implemented after approval of the EC.

A deviation is any instance(s) of failure to follow, intentionally or unintentionally, the requirements of the protocol. Under emergency circumstances, deviations from the protocol to protect the rights, safety, and wellbeing of human subjects may proceed without prior approval of the Sponsor and the EC/competent authority (CA). Such deviations shall be documented and reported to the Sponsor and the EC as soon as possible. Deviations will be reported as:

**Critical Deviations:** Deviations that significantly affect the safety, efficacy, integrity, or conduct of the study. These deviations must be reported to the Sponsor no later than 5 working days from awareness of occurrence and reported to the EC per the deviation reporting policy.

**Non-Critical Deviations:** Protocol deviations that do not significantly affect the safety, efficacy, integrity, or conduct of the clinical investigation. These deviations must be documented on the CRF Protocol Deviation page and will be reviewed by the sponsor.

Non-substantial modifications may be made during the normal course of device optimization, maintenance, and feasibility testing. Non-substantial modifications will be communicated to the CA as soon as possible, if applicable, and to the EC per their policy.

### 11.4 Participant Information and Informed Consent

The bioethics committee was provided with and has approved the reasoning and documentation regarding the disbandment of informed consent forms during this clinical investigation. The reasons that were provided and were found to be sufficient for the disbandment are as follows:

- The informed consent forms of subjects who had had a 2D TTE exam performed and the resulting DICOM study saved in the investigation site's database during the time period from 2010-08-01 to 2020-08-01 would be inconsequential, because before the commencement of the analysis of the data all personal information from the DICOM studies will be removed by the IT specialists in the investigation's site. Therefore, the probability of identification of the subjects during analysis is close to zero and such consequences of the unlawful and damaging identification of subjects would require irrational amount of resources.
- The retrospective analysis of DICOM images will not affect the subjects for whom the 2D TTE examination was performed in any way as no new medical procedures would be performed, no side effects are possible, and no personal information would be accessed by either the researchers, or the sponsor.
- Often it would require unreasonable resources or would be impossible to trace back and contact the subjects for whom the 2D TTE examinations were performed due to difficult current health or social status, unreachable/unknown/incomplete contact information.

### 11.5 Early Termination of the Study

The Sponsor may terminate the study prematurely according to certain circumstances. Examples of such circumstances include ethical concerns, insufficient participant recruitment, participant safety concerns, alterations in accepted clinical practice that make the continuation of a clinical investigation unwise, early evidence of benefit or harm of the research product, or for any other reason.

## 12 Statistical Methods

### 12.1 Statistical Hypotheses

UAB Ligence	Clinical Investigation Report	2021-04-09
		Rev: 1.0

The following hypotheses will be tested with the statistical methods:

1. The manual functionalities of Ligence Heart provide equally accurate tools for echocardiography evaluation compared to other state of the art CE marked medical software.
2. Automatic functionalities of Ligence Heart software perform echocardiography image analysis with non-inferior accuracy compared to a cardiologist.
3. Automatic functionalities of Ligence Heart software perform echocardiography image analysis with lower intra-rater variability compared to a cardiologist.
4. Automatic functionalities produce measurement values faster than a cardiologist.

## 12.2 Sample Size Determination

Required sample size was established with the help of statistical power calculation tool „G\*Power 3.1.9.7“, which estimates the minimum sample size required to find and statistically prove if there is an effect to be found. In the analyses that were carried out the sample size was calculated for Repeated measures, within-between interaction ANOVA. Obtained minimal sample size was established to be 54 for both Part 1 and Part 2 of the clinical investigation (Variables used in calculations are provided in the table below).

Sample size determination variables

Coefficient	Value
Effect Size	0.25
$\alpha$	0.05
Power (1 - $\beta$ )	0.95
Number of groups	3
Number of measurements	2
Correlation among repeated measures	0.6

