### 6.3 Number of Subjects

Required sample size was established with the help of statistical power calculation tool „G\*Power 3.1.9.7“, which estimates the minimum sample size required to find and statistically prove if there is an effect to be found. In the analyses that were carried out the sample size was calculated for Repeated measures, within-between interaction ANOVA. Obtained minimal sample size was established to be 54 for both Part 1 and Part 2 of the clinical investigation (Variables used in calculations are provided in the table below).

Coefficient	Value
Effect Size	0.25
$\alpha$	0.05
Power (1 - $\beta$ )	0.95
Number of groups	3
Number of measurements	2
Correlation among repeated measures	0.6

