## 7.2 Subject Procedure

### Part 1

The purpose of the procedure in the Part 1 is to calculate the accuracy of Ligence Heart manual functions that are used to perform echocardiographic measurements comparing it with the accuracy of manual measurements performed with other CE marked state-of-the-art medical image viewers. Measurements made in Ligence Heart software will be compared with CE marked software “IntelliSpace Cardiovascular 5.1” (Phillips) and “EchoPAC” version 112 from GE Healthcare.

One cardiologist will perform 2D TTE measurements of each patient on each system 2 times. Time difference between repeated measures must be at least two days.

### Part 2

The purpose of the procedure in the Part 2 is to compare Ligence Heart automatic measurements accuracy and reliability with human cardiologists in real clinical setting.

Four physicians will make 2D TTE measurements of each subject study 2 times. Physicians cannot share thoughts or results between themselves. Time difference between repeated measures must be at least two days. Measurements of three physicians will be used in modeling and results of the 4th will be used as a validation with automated system.

During both parts, time used for the analysis of the 2D TTE images will be recorded. During manual 2D TTE image analysis, time it takes for physician to make measurements will be registered. Stopwatch starts when physician opens study in Ligence Heart and stops when all listed measurements are made. In the use case including automatic measurements, the time it takes for automatic system to make measurements and physician to correct/validate the results is registered.

Summary of the clinical investigation parts

#	Analysis	Purpose	TTE Examination Protocol	Measurements
Part 1	Manual Measurement Analysis	To calculate the accuracy of Ligence Heart manual functions that are used to perform echocardiographic measurements comparing it with the accuracy of manual measurements performed with other CE marked state-of-the-art medical image viewers.	One physician will make 2D TTE measurements of each patient on each system 2 times. Time difference between repeated measures must be at least two days.	
 
• AoS (PLA)
 
• RVB (A4CH)
 
• LVEDV (A4CH)
 
• LVEDV (A2CH)
 
• RVEDA (A4CH)
 
• RAA (A4CH)
 
• AV-Vmax
 

UAB Ligence	Clinical Investigation Report	2021-04-09
		Rev: 1.0

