### 16.2 Automatic functionalities (Part 2)

Due to the fact that echocardiography is prone to considerable inter- and intra-observer variability, it was important to perform comparison of the automatic measurements using data from multiple board certified cardiologists. The first three cardiologists established the acceptable intra- and inter-observer variation ranges while the fourth cardiologist and Ligence Heart were used as independent raters with accuracy calculated as the number of times measurements fell within acceptable variation range in the selected studies. Non-inferiority of automatic measurements accuracy to a cardiologist was established by conducting the t-test and assuring p-values are  $> 0.05$  which proves that any differences are non-significant. All of the measurements passed the required performance threshold, and for 7 out of 21 automatic measurements, both Ligence Heart and FC had full agreement with the ORG.

Conversely, Ligence Heart automatic functionalities did not return a value for at least one study in 11 measurements, however, there was a sufficient number of studies for all measurements where automatic analysis value was returned to ensure statistical power. The reason for no value being returned in a particular study has to do with the automatic predictions not passing quality thresholds which are employed in each step of the automatic functionalities (classification, cardiac phase or cycle detection and measurement prediction confidence). This ensures that a lower number of false values is provided to the user of the medical device and serves as a safety mechanism by reducing the number of potential false positive findings.

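### N = 54 and power 0.95 reproduce, but only for a group-by-repeat interaction in three separate patient groups, a test the study does not perform; they give no support to the equality and non-inferiority claims

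*Protocol*

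**What the plan says.** Section 12.2, repeated in section 6.3, names the test used for sizing: "In the analyses that were carried out the sample size was calculated for Repeated measures, within-between interaction ANOVA". The inputs are effect size 0.25, α 0.05, power 0.95, correlation among repeated measures 0.6, "Number of groups 3" and "Number of measurements 2". The result is given as follows: "Obtained minimal sample size was established to be 54 for both Part 1 and Part 2 of the clinical investigation".

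The design in sections 7.1 and 7.2 is fully crossed. In Part 1, "One cardiologist will perform 2D TTE measurements of each patient on each system 2 times". In Part 2, four physicians read every study twice. Three of them enter the model, and the fourth is set beside the automated system. The ANOVA tables in 12.4.1 and 12.5.1 carry patient-by-software and patient-by-cardiologist terms.

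Section 12.1 lists four hypotheses: equal accuracy of the manual tools, non-inferior accuracy of the automatic ones, lower intra-rater variability, and shorter time. No margin for equality or non-inferiority appears anywhere in the document.

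Section 16.2 says of the studies in which the software returned no value: "there was a sufficient number of studies for all measurements where automatic analysis value was returned to ensure statistical power".

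**The concern.** In the named G*Power procedure, groups are a between-subject factor: different patients in each group. The tested effect is whether the change from the first to the second measurement differs between groups. The study has no between-patient groups, and no hypothesis concerns such a difference in change. The 0.95 is therefore not the power of any hypothesis in section 12.1.

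There is a second gap. Power to detect a difference does not carry over to a claim of equality or non-inferiority, which needs a margin. Two of the four hypotheses are claims of that kind. In Part 2 the device and the fourth cardiologist also stand outside the ANOVA, so that model does not test hypothesis 2 at all.

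At stake is whether a reader may take the Part 2 non-inferiority conclusion as resting on a study sized for it, and whether the reassurance in 16.2 about non-returned values has a basis.

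**Working it through.** **Inputs (12.2):** f = 0.25, α = 0.05, ρ = 0.6, k = 3 groups, m = 2 measurements, N = 54.

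**1. The plan's own figure.** For the within-between interaction:
- λ = N·f²·m/(1 − ρ) = 54 × 0.0625 × 2 / 0.4 = 16.875
- df1 = (k − 1)(m − 1) = 2; df2 = (N − k)(m − 1) = 51
- Noncentral F gives power 0.9555. At N = 51 it is 0.943.

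So 54 is the smallest multiple of 3 that reaches 0.95. It is a total, 54/3 = 18 different patients per group.

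**2. Same inputs in the crossed design.** One group of patients, within-patient main effect over three systems (m = 3):
- λ = 54 × 0.0625 × 3 / 0.4 = 25.31; df 2 and (54 − 1) × 2 = 106; power 0.996 (35 patients would reach 0.95).
- With two levels: λ = 16.875, df 1 and 53, power 0.981.

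For a difference test, 54 is more than enough on the plan's own inputs.

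**3. Non-inferiority in Part 2.** The document gives no margin, so margin and true agreement are assumptions here. I take agreement with the original raters as the outcome, as in Table 3. I assume the same true agreement of 97–99% for the device and the fourth cardiologist, independent readers, and a two-sided 95% Newcombe lower limit that must lie above minus the margin. Exact enumeration gives:

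| Margin (points) | n = 54, 98% (range 97–99%) | n = 58, 98% |
|---|---|---|
| 5 | 23% (19–24%) | 26% |
| 7.5 | 45% (37–61%) | 45% |
| 10 | 77% (66–91%) | 76% |
| 15 | 96% (93–99%) | 99% |

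The first row is low for a simple reason. If both readers agree in 54 of 54 studies, the Wilson lower limit for each is 54/(54 + 1.96²) = 54/57.84 = 0.934. The lower limit for the difference is then −(1 − 0.934), about −6.6 points. A perfect result in both readers would not exclude a 5-point deficit.

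A paired score test over 95–99% agreement gives a similar picture at n = 54: 15–25% at 5 points, 52–91% at 10, 85–99% at 15. If the two readers' failures correlate at 0.5, it gives 18–25% at 5 points and 72–97% at 10.

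**4. Table 3 on the same scale.** LAD is 55/58 against 58/58, with a lower limit of about −14 points. RAA is 51/54 against 53/54, about −13 points. Both are marked as passing.

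**5. Section 16.2.** The smallest number of studies in Table 3 is 54, equal to the planned minimum. No other power basis appears in the document.

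**The case against.** - *The study is more than large enough for the difference test in 12.4.2.* This stands. A reader might infer that the wrong choice of ANOVA left the study underpowered, or that 54 is miscalculated. Neither follows: the calculation is correct for its test, and the crossed difference test has 0.996.
- *Non-inferiority power cannot be called far lower than 0.95, because no margin is given.* This also stands. That stronger reading is tempting and would be true for margins up to about 7.5 points, but at 15 points power reaches 93–99%. The supportable word is undetermined.
- *The minimal detectable change in 12.5 serves as the margin.* It does not. It is a limit for a single reading and decides whether that reading counts as in agreement. It does not say how far the device's agreement rate may fall below the cardiologist's.
- *Section 16.2 names no number.* Correct. That it leans on 54 is an inference, made plausible by the minimum of 54 in Table 3. It remains true that sections 6.3 and 12.2 are the only power basis in the document.
- *With results in hand, restated power changes no estimate, and taking p > 0.05 as proof of non-inferiority is the larger fault.* That rule is a separate matter, but it makes power more relevant, because under it a weak comparison helps the device pass. At n = 54, with independent readers and a pooled z test, a device truly at 90% against 98% would pass about 59% of the time.

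**Conclusion.** Wrong as written. The fault is a mismatch between the sizing model and the study's design and hypotheses, not an arithmetic error. The figure of 0.95 belongs to an interaction across three separate patient groups and to none of the four hypotheses. It lends no support to the Part 1 equality claim or the Part 2 non-inferiority claim, and the power statement in 16.2 is left without a basis.

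The power of those two claims cannot be determined from the document. For Part 2 it runs from about one in five to nearly certain as the margin goes from 5 to 15 points. That range applies to each measurement singly and rests on the assumed agreement rates, independent readers and the Newcombe limit. No corresponding range is given for Part 1, where the document offers neither a margin nor a variance to compute from.

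**What to change.** 1. In 6.3 and 12.2, say that 54 came from a three-group interaction model that is not the analysis, and withdraw 0.95 as the study's power.
2. State and justify a margin for the paired Part 2 comparison of device and fourth cardiologist, and another for Part 1 equivalence. Give the power at 54 to 58 studies for each.
3. If no margin can be justified, give the expected confidence-interval half-width for the paired difference instead.
4. Strike or correct the power sentence in 16.2.

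The cost is wording and one calculation. The stated power is likely to become less favourable. Whether 54 to 58 studies suffice will depend on the margin chosen, so it cannot be promised in advance that no more are needed.
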